8 BACKGROUND INFORMATION AND RATIONALE

8.1 Background

Perthes' disease is an idiopathic avascular necrosis in a developing femoral head (ball of the hip joint). It occurs predominantly in males (male:female ratio 4:1) between 4 and 12 years old [1, 2]. The disease results in collapse of the bone within the femoral head, which results in severe pain and disability amongst affected children. Severe pain and disability continues until the hip re-ossifies; which is typically after 2-3 years [3]. Perthes' disease typically results in long-term deformity of the hip, which can cause longer term pain and disability and is a major precipitant of premature osteoarthritis; frequently necessitating a hip replacement in early adulthood [4]. Perthes' disease is one of the most common and most poorly understood disorders encountered by children's orthopaedic surgeons.

The UK has the highest incidence of Perthes' disease in the world, with children in Northern England, and particularly Liverpool, having the greatest risk of disease [2, 5, 6]. The lifetime cumulative risk of disease in the UK is around 1:1200 children, with around 500 new cases in the UK each year [6]. The origins of the disease are very closely linked to socioeconomic deprivation [2, 6, 7], though the aetiology and mechanism are unknown.

A key principle of Perthes' disease treatment is a process called 'containment'. As the head of the femur collapses, the belief is that it should be 'contained' within the acetabulum in order to allow it to re-ossify (re-develop) in the round shape of the acetabulum. Some surgeons perform surgery to facilitate 'containment' by redirecting the femoral head into the acetabulum (i.e. a femoral osteotomy, typically with a plate & screws and a 'spica' plaster cast) and others will direct/alter the shape of the acetabulum to better cover the femoral head (i.e. pelvic osteotomy, typically with internal wires and a 'spica' plaster cast); soft tissue releases (i.e. tendon releases) may also be performed to improve the range of movement. However, other surgeons believe that a package of care including physiotherapy, activity restriction and pain relief is equally as good at achieving 'containment'; called 'active containment'. This causes international controversy and uncertainty for children and their parents/carers.

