9.4 Secondary objectives and outcome measures

Table 7: Secondary objectives and outcome measures

| Objective | Outcome measure | Time point(s) of evaluation of this outcome measure (if applicable) | Data required | Source data (including location) |
|---|---|--|--------------------------------------|--|
| To compare lower extremity function in both groups | PROMIS Mobility CAT | Baseline and 3, 6, 9, 12, 18, 24, 30 and 36 months post randomisation | PROMIS mobility score | Case report Form (entered directly into the REDCap study database) |
| To compare pain levels in both groups | Wong Baker Faces Pain Scale | Baseline and 3, 6, 9, 12, 18, 24, 30 and 36 months post randomisation | Wong Baker Faces Pain Scale score | Case report Form (entered directly into the REDCap study database) |
| To compare Quality of Life, Activities of Daily Living, Sleep and Psychological Impact in both groups | CHU-9D Questionnaire | Baseline and 3, 6, 9m 12, 18, 24, 30 and 36 months post randomisation | CHU-9D score | Case report Form (entered directly into the REDCap study database) |
| To compare impact on family life in both groups | PROMIS family relationships tool | Baseline and 3, 6, 9, 12, 18, 24, 30 and 36 months post randomisation | PROMIS family relationships score | Case report Form (entered directly into the REDCap study database) |
| To compare educational participation in both groups | Non validated questionnaire on school absence | 3, 6, 9, 12, 18, 24, 30 and 36 months post randomisation | Days of school absence | Case report Form (entered directly into the REDCap study database) |

| Objective | Outcome measure | Time point(s) of evaluation of this outcome measure (if applicable) | Data required | Source data (including location) |
|---|--|--|--|--|
| To compare the complication rate, particularly considering the need for future operative interventions in both groups | Non validated questionnaire on complications | 6, 12, 18, and 36 months post randomisation | Frequency of pressure sores, non-union of the bone, wound or bone infection, major injury to nerves altering lower limb function, implant-related fracture, metalwork fracture/failure, need to remove/adjust metal implants, total hip arthroplasty (replacement) | Case report Form (entered directly into the REDCap study database) Medical notes |

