PROMIS Pediatric Family Relationships [25] - This has been highlighted as an important outcome within the core outcome set. The complex role of families in child and adolescent health and their role in the management of chronic conditions however has been hampered by a lack of validated measures of family relationship experiences. This instrument addresses this gap, with item banks and short forms developed using a rigorous mixed-method approach consistent with PROMIS standards.

Educational participation - Parents will be asked to indicate the number of days their child did not participate in educational activities due to their Perthes' disease.

Complications - All complications related to the disease and its treatment will be recorded. The complications anticipated in the management of these patients (particularly considering readmission or subsequent surgery) include pressure sores, non-union of the bone, wound or bone infection, major injury to nerves altering lower limb function, implant-related fracture, metalwork fracture/failure, need to remove/adjust metal implants, total hip arthroplasty (replacement).

Resource use - Participants' use of primary, secondary and community care services, as well as medications will be collected using a bespoke electronic resource use questionnaire. In addition, parental absence from work and additional days of purchased childcare will be collected.

Radiographs - This study will harvest routinely collected images of the hip/ pelvis available on the Picture Archiving and Communication System (PACS) taken pre-operatively, post-intervention and the most recent at 3 years post randomisation. These routine images will be stored in a bespoke application (TRIAGE) hosted at the University of Oxford and used to quantify the degree of residual deformity by an independent assessor, using the Stulberg classification for all hips in the Waldenstrom 3B (late re-ossification) or 4 (healed) stage of disease.

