21.3 Expected adverse events

This is a low risk, pragmatic trial where both of the study interventions are in common use. For this trial, foreseeable AEs will not need to be reported immediately, but will be recorded on participant and site reported CRFs. They include the following (including the need for hospital admission and/or further unplanned surgery to manage these complications in either group):

The complications anticipated in the management of these patients (particularly considering readmission or subsequent surgery) include pressure sores, non-union of the bone, wound or bone infection, major injury to nerves altering lower limb function, implant-related fracture, metalwork fracture/failure, need to remove/adjust metal implants, total hip arthroplasty (replacement).

² Medical events that may jeopardise the participant or may require an intervention to prevent one of the above characteristics/consequences.

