23.2 Sample Size/Power calculations

172 participants providing data on the PROMIS Mobility Score for children at three years post randomisation (86 in each group) will provide 90% power to detect a difference in means of 5, assuming the standard deviation (SD) is 10 using a two group t-test with a 5% (2-sided) significance level. This is inflated to 216 participants (108 per arm) to allow for 20% attrition.

Raw scores of the PROMIS are translated into standardised T-scores with a population mean of 50 and an SD of 10.

The minimum clinically important difference (MCID) of PROMIS paediatric measures is generally 3.0-5.0 [29,30].

We discussed with children and families the size of the difference they would require to justify surgery, over optimised non-surgical containment. Given that surgery is a considerable intervention in the lives of the child and their family (i.e., the anaesthetic, the pain and scar, admission to hospital, the frequency of the requirement for a second procedure to removal metalwork, along with the lengthy

duration of immobilisation and recovery), families believed that the effect sought should be at the upper range of the MCID. Other studies have similarly highlighted that patients often seek greater effect sizes to warrant bigger surgical interventions than the established MCID [31].

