23.3.2 Secondary outcome(s)

Continuous secondary outcomes measured over time (PROMIS Mobility over time, Wong-Baker Faces Pain Scale, CHU-9D and PROMIS Family Relationships) will be compared using a multi-level mixed effects linear regression model with repeated measures (level 1) grouped within participants (level 2). Models will include treatment, baseline score, time-by-treatment interaction and minimisation factors as fixed effects. Educational participation will be analysed as total days missed during the 3 year follow up using a Negative Binomial regression model, adjusting for treatment and minimisation factors as fixed effects. Degree of residual deformity will be analysed as Stulberg grade at 3 years follow up using an ordinal logistic regression model, adjusting for treatment and minimisation factors as fixed effects. The number and proportion of participants experiencing each type of complication will be summarised by treatment group. Heterogeneity by centre will be explored visually using forest plots and with a sensitivity analysis on the primary outcome where statistical models applied will also adjust for centre as a random effect.

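### The complication item for removing or adjusting metal implants does not separate planned from unplanned removal, so its row would mix expected further surgery with harm

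*Protocol*

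**What the plan says.** The objective in section 9.4, Table 7, is "To compare the complication rate, particularly considering the need for future operative interventions in both groups". The data listed for it end with "need to remove/adjust metal implants, total hip arthroplasty (replacement)". Section 9.5 repeats the list, introduced by "The complications anticipated in the management of these patients (particularly considering readmission or subsequent surgery) include pressure sores". Section 21.3 repeats it again as foreseeable adverse events, and adds that these include hospital admission and "further unplanned surgery to manage these complications in either group".

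Elsewhere the protocol treats implants and their removal as a usual part of surgery. Section 8.1 describes "femoral osteotomy, typically with a plate & screws and a 'spica' plaster cast", and internal wires for pelvic osteotomy. Section 23.2 explains why families wanted a large benefit before accepting surgery, and cites "the frequency of the requirement for a second procedure to removal metalwork" alongside the anaesthetic, the scar and the recovery.

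The planned analysis, in section 23.3.2, is: "The number and proportion of participants experiencing each type of complication will be summarised by treatment group". No combined rate and no test is specified for complications.

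**The concern.** The item is defined by the need for a procedure and not by the reason for it. A child whose osteotomy has healed and whose plate is removed electively can be entered under it, and so can a child whose plate comes out early because something went wrong. The first is a further operation that families are told to expect; the second is harm.

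Implants come from surgery, so the item will arise almost entirely in the surgery arm. A reader of the final table could not tell how much of the difference in that row is harm and how much is expected further surgery. Both matter in weighing surgery against active containment, but they answer different questions. The distinction is easy to record at the time and hard to recover later without returning to the medical notes.

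**Working it through.** The protocol states no complication rate and no metalwork-removal rate, so there is no figure of its own to reproduce on this point. Its one calculation, the sample size in section 23.2, does not depend on this item. It reproduces: the t-test needs 85.03 per arm, rounded up to 86, with power 0.903, and 172 / 0.8 = 215, or 216 in equal arms.

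**Step 1: does any wording exclude planned removal?**
- Sections 9.4 and 9.5: no qualifier on the item.
- Section 21.3: the word unplanned describes surgery done to manage the listed complications. Metalwork removal is itself on that list, so the word does not clearly limit the item.
- Section 21.2 defines an adverse event as an untoward occurrence. That argues against counting a planned removal as an adverse event, but Table 7 does not tie the complications questionnaire to that definition.
- Section 23.2 speaks of a requirement for removal, much the same term as the need in Table 7, when it describes the frequent second procedure. The word need therefore does not settle the matter.

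The item is undefined on this point.

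**Step 2: what would the by-type table show?** Take three illustrative children.

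| Child | Event | Rows entered |
|---|---|---|
| A | Planned plate removal after healing, 15 months | Metalwork row (if planned removal counts) |
| B | Plate removed for infection, 4 months | Metalwork row and infection row |
| C | Unplanned removal for symptoms, no other listed event | Metalwork row |

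B's infection is visible on its own line, as would be non-union, a fracture related to the implant or failure of the metalwork. A and C look the same. The count in the metalwork row covers all three without distinction.

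**Step 3: which arm?** Implants in the randomised hip follow surgery, so the item falls mainly in the surgery arm. There are two exceptions: cross-over to surgery, which section 13.4 expects, and implants in a non-study hip. Section 11.3 admits bilateral disease, and section 11.4 excludes prior containment surgery only on the hip to be randomised.

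**Step 4: possible size, on assumed inputs only.** Let m be the share of the 108 surgery-arm children with implants, r the share of those with planned removal by 36 months, and c the proportion with any other listed complication. Assume m = 50-100%, r = 20-80%, c = 5-10%, and independence between planned removal and other complications.
- Added to the metalwork row: 108 × m × r. Low: 108 × 0.5 × 0.2 = 10.8. High: 108 × 1.0 × 0.8 = 86.4.
- Any-complication proportion, if one were reported: 1 − (1 − c)(1 − m × r). Low: 1 − 0.95 × 0.90 = 14.5% (15.7 of 108), against 5% (5.4) without planned removal. High: 1 − 0.90 × 0.20 = 82% (88.6 of 108), against 10% (10.8).

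These figures treat all 108 allocated children as having surgery; section 13.4 expects some will not, which lowers them.

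**The case against.** A reader might infer that the protocol has a rule scoring every routine removal as harm and so inflates the surgery arm's complication rate. The documents do not support that. The list does not mention routine or planned removal. Section 23.2 calls the second procedure frequent without saying how often it is planned, and the untoward-occurrence definition in section 21.2 can be read as leaving planned removal out. Section 23.3.2 specifies a descriptive summary by type, so no pooled rate is defined that could be inflated; only the word rate in the Table 7 objective hints at one.

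Nor can it be said that real safety signals are hidden in general. Infection, non-union, implant-related fracture and metalwork failure each have their own line, and only removals for other reasons, such as symptoms, do not.

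Counting second operations is also intended: the objective names future operative interventions, and families weighed the second procedure when judging what benefit would justify surgery. A difference between arms in metalwork removal is a real consequence of treatment. Finally, the complications form is not shown. Appendix 2 gives only the heading, and a planned/unplanned field may already exist.

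All of this stands, and it limits the point to one undefined row. It does not remove it. The same row can still hold expected and unexpected removals, and wanting to count second operations is a reason to label them clearly.

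**Conclusion.** The point holds as a minor clarification. The item does not separate planned removal after healing from unplanned removal or adjustment, although the protocol describes a second procedure to remove metalwork as frequent. The metalwork row would therefore mix expected further surgery with harm, almost entirely in the surgery arm, and so would any overall complication rate derived from the Table 7 objective. Nothing else is touched: not the other complication rows, the primary outcome or the sample size.

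The documents give no rate from which to size the effect. The range of about 11 to 86 of 108 children rests wholly on the assumed shares, and is wide enough to show only that the row could be dominated by planned removals or changed modestly. The any-complication figures apply only if such a rate is reported, which the analysis section does not plan.

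**What to change.** In Table 7, sections 9.5 and 21.3, and the Complications CRF, record each metalwork removal or adjustment as planned or unplanned, with the reason. If the form already has such a field, the protocol text needs only to say so. Report unplanned removal or adjustment as a complication, and planned removal by arm as a further operation. State that any overall complication rate excludes planned removal. Every second operation then stays visible, as the objective intends.

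The cost is one extra CRF field that site staff must classify and one extra table row. The field should be in place at collection, because Table 9 has complications reported by participants at 6, 12, 18 and 36 months and by sites only at 18 and 36 months, and a mixed row cannot be separated afterwards without going back to the notes. The change concerns recording and reporting only and prescribes no clinical practice.

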9.5 Choice of secondary outcomes

PROMIS Mobility. As per section 9.3 Choice of primary outcome/justification for the follow-up period

Wong-Baker FACES Pain Scale [20] - The Wong-Baker faces pain score is a validated self-reported tool that will be self-reported amongst all children in the study. It is an ordinal assessment of pain outcomes, using a series of six facial-expressions to illustrate the degree of pain intensity. A numerical rating is assigned to each face (from 0 - 'no hurt' to 10 – 'hurts worst'). It has been validated for use amongst children over 3-years-old, including in the Emergency Department setting [21]. It is particularly useful in children, as only one third of children up to 14 years understand the concept of a visual analogue scale [22]. The Wong Baker Faces Pain Score has been demonstrated to be useful in older children aged 8-17 years old, correlating closely with other pain tools, such as VAS [21]. The OP Non-STOP study team have also used this scale previously and found almost identical scores amongst children <8 years and those aged 8-16 [23]. This tool has the advantage that it can be self-reported amongst all participants in the study as it is validated for self-reported use from 5 years old [16, 17].

Child Health Utility-9D (CHU-9D) [24]. - The CHU-9D is a paediatric preference-based measure of health-related quality of life, consisting of 9 domains each with a 5-level response. This will be used to elicit health utility for the cost-utility analysis. For consistency with the primary outcome measure we intend to conduct all measurements via proxy. Valuation will estimate Quality-adjusted life-years (QALYs) using an area under the curve approach with preference weights derived for the UK population. In addition to the cost utility analysis, we will report the components of CHU-9D separately as these measure several elements of health that families have indicated that they are particularly interested in, through the core outcome set (i.e. sleep disturbance, psychological impact and activities of daily living).

PROMIS Pediatric Family Relationships [25] - This has been highlighted as an important outcome within the core outcome set. The complex role of families in child and adolescent health and their role in the management of chronic conditions however has been hampered by a lack of validated measures of family relationship experiences. This instrument addresses this gap, with item banks and short forms developed using a rigorous mixed-method approach consistent with PROMIS standards.

Educational participation - Parents will be asked to indicate the number of days their child did not participate in educational activities due to their Perthes' disease.

Complications - All complications related to the disease and its treatment will be recorded. The complications anticipated in the management of these patients (particularly considering readmission or subsequent surgery) include pressure sores, non-union of the bone, wound or bone infection, major injury to nerves altering lower limb function, implant-related fracture, metalwork fracture/failure, need to remove/adjust metal implants, total hip arthroplasty (replacement).

Resource use - Participants' use of primary, secondary and community care services, as well as medications will be collected using a bespoke electronic resource use questionnaire. In addition, parental absence from work and additional days of purchased childcare will be collected.

Radiographs - This study will harvest routinely collected images of the hip/ pelvis available on the Picture Archiving and Communication System (PACS) taken pre-operatively, post-intervention and the most recent at 3 years post randomisation. These routine images will be stored in a bespoke application (TRIAGE) hosted at the University of Oxford and used to quantify the degree of residual deformity by an independent assessor, using the Stulberg classification for all hips in the Waldenstrom 3B (late re-ossification) or 4 (healed) stage of disease.

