| To estimate cost- effectiveness, from the UK NHS and Personal Social Services perspective in both groups | Non validated resource use questionnaire and CHU-9D | Baseline (CHU-9D only), 6, 9, 12, 18, 24, 30 and 36 months post randomisation | Resource use from hospital and out of pocket expenditure from families. CHU-9D score | Case report Form (entered directly into the REDCap study database) |
| To quantify the degree of residual deformity (waldenstrom grade and Stulberg classification) | Measured from routinely collected images of the hip or pelvis harvested from the picture archiving system. | An image of the hip or pelvis harvested from the picture archiving system within a 6 month timeframe of the primary outcome (36 months). | Routinely collected images of the hip or pelvis harvested from the picture archiving system. | Medical notes |

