10.6 Central review procedures

The degree of residual deformity will be quantified (Waldenström grade and Stulberg classification) on the central review CRF.

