11.3 Inclusion Criteria

A patient will be eligible for inclusion in this study if **ALL** of the following criteria apply:

- Radiographic evidence of Perthes' disease,
- Radiographs demonstrate that the disease is in the initial, sclerotic or fragmentation stage,
- Aged 5 to 12 years inclusive,
- Willing and able to give informed assent/consent.

Note: Patients may be enrolled with bilateral Perthes' Disease - though patients can only ever be enrolled once into the study. If one side has old disease (i.e. hip in reossification or healed stage of disease) and is not already included in the study, then the newly affected hip can be enrolled (i.e. that hip in the initial, sclerotic or fragmentation stage). If both hips have new disease, then the hip considered the most severely affected will be considered the hip of interest and the surgeon must specify which hip is the unit of randomisation.

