Sourced/Collected by Local Research Team in a clinic visit / telephone call

- Date
- Complications/SAE review
- All radiographic images collected as part of routine practice will be harvested and given to the study team. In particular, images taken pre-operatively, post-intervention and as close as possible to the 3 year post intervention date will be collated.

Direct Participant Report (collected electronically)

- Patient assessment of function
 - o PROMIS Mobility CAT
- Pain
 - o Wong-Baker FACES Pain Scale
- Quality of life
 - o CHU-9D
- Impact of the condition
 - o Resource use
 - Complications
 - o Participation in Education
 - o PROMIS Pediatric Family Relationships Questionnaire

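### Stulberg grade is compared by arm only in hips that have reached Waldenström 3B or 4, a state reached after randomisation, and the protocol has no rule for hips not yet there

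*Protocol*

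**What the plan says.** - **Entry (section 11.3):** "Radiographs demonstrate that the disease is in the initial, sclerotic or fragmentation stage". No randomised hip has begun to re-ossify.
- **Time course (section 8.1):** "Severe pain and disability continues until the hip re-ossifies; which is typically after 2-3 years".
- **Who is graded (section 9.5, Radiographs):** an independent assessor quantifies residual deformity "using the Stulberg classification for all hips in the Waldenstrom 3B (late re-ossification) or 4 (healed) stage of disease".
- **What is recorded (section 10.6):** "The degree of residual deformity will be quantified (Waldenström grade and Stulberg classification) on the central review CRF".
- **What is analysed (section 23.3.2):** "Degree of residual deformity will be analysed as Stulberg grade at 3 years follow up using an ordinal logistic regression model", adjusted for treatment and the minimisation factors. No between-arm analysis of Waldenström stage is named.
- **Population and missing data (sections 23.4 and 23.8):** available data in randomised groups. Missing data are summarised and their patterns examined. Multiple imputation is a sensitivity analysis, used if missingness is sufficient or differential.
- **Image date:** Table 7 (section 9.4) asks for a routine image "within a 6 month timeframe of the primary outcome (36 months"). Sections 9.5 and 20 also count three years from randomisation. Appendix 2, at 36 months, wants the image "as close as possible to the 3 year post intervention date will be collated".

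**The concern.** Whether a hip has reached 3B or 4 at 36 months is settled after randomisation. A comparison limited to those hips is a comparison of two subsets, and randomisation does not guarantee that the subsets are alike. If one arm brings more hips to 3B/4, and hips with worse deformity get there later, that arm contributes more poor hips to the analysis and can look worse with no real difference in shape. Adjusting for age, sex and lateral pillar height removes only what those factors explain.

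Section 8.3 says surgeons give weight to femoral head shape as a guide to how long the hip will last, so this result will be read closely even though it is secondary.

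The image date is a smaller, separate matter. A date counted from intervention moves with any delay to treatment and is undefined for a child who receives no intervention. Section 13.4 expects some children allocated to surgery not to have it.

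**Working it through.** **1. The plan's own figure.** The protocol gives no expected number of gradable hips. Its only sample-size figure is for the primary outcome (section 23.2: difference 5, SD 10, 90% power, two-sided 5%).
- Normal approximation: n per arm = 2 × (1.960 + 1.282)² × 10² / 5² = 84.1, so 85.
- Two-sample t-test: 85.03, so 86 per arm, 172 in all. Power at 86 per arm is 90.3%.
- Attrition: 86 / 0.8 = 107.5, so 108 per arm, 216 in all. The figure reproduces.

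**2. Number graded.** This uses 172 as a stand-in for children with a usable image; the 20% attrition was set for PROMIS Mobility, not for radiographs. The share at 3B/4 is assumed, because the documents give none.

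| Share at 3B/4 | 90% | 80% | 70% | 60% |
|---|---|---|---|---|
| Graded, of 172 | 155 | 138 | 120 | 103 |

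**3. Possible bias with no true effect.** Assumptions, none of them from the documents:
- latent deformity u ~ N(0,1) in both arms, cut into five grades holding 10/25/30/25/10%;
- logit P(3B/4) = a_arm − b·u, with a_arm set to give the stated share in each arm;
- proportional-odds model of grade on arm, fitted to gradable hips only.

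The table gives the large-sample odds ratio for a worse grade in the arm with the larger share, by numerical integration. Random-draw simulation agrees to within about 0.02.

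| Slope b (log-odds per SD) | equal shares | 85% v 75% | 90% v 75% | 90% v 70% |
|---|---|---|---|---|
| 0.3 | 1.00 | 1.05 | 1.08 | 1.11 |
| 0.5 | 1.00 | 1.08 | 1.13 | 1.18 |
| 1.0 | 1.00 | 1.16 | 1.24 | 1.34 |
| 1.5 | 1.00 | 1.21 | 1.33 | 1.47 |

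A weaker link gives less. If grade depends on u plus logistic noise, with slopes 0.5-1.0 and shares differing by 10-20 points, simulated odds ratios run from 1.03 to 1.14 and the nominal 5% type I error becomes 5.1% to 6.9%.

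**4. Against sampling error.** With about 70 graded hips per arm and the same grade distribution, Σp³ = 0.060 and SE(log OR) = √[3 × 140 / (70 × 70 × (1 − 0.060))] = 0.30.
- For OR 1.24: ln 1.24 = 0.215, or 0.71 SE. Type I error ≈ Φ(−2.67) + Φ(−1.25) ≈ 11%.
- For the extreme OR 1.47: ln 1.47 = 0.385, or 1.28 SE. Type I error ≈ Φ(−3.24) + Φ(−0.68) ≈ 25%.

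**5. Image date.** Table 7 and sections 9.5 and 20 use 36 months or three years from randomisation; Appendix 2 uses three years from intervention. Surgery is typically within three months of randomisation (section 13.1), so the usual shift is up to about three months.

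**The case against.** **The causal premise is not in the documents.** A reader might infer that the faster-healing arm will look worse, or that the randomised comparison is lost. The text does not support that. The rationale in section 8.1 is that the head is contained "in order to allow it to re-ossify (re-develop) in the round shape of the acetabulum", which concerns shape and not speed. Section 8.2 reports that the earlier national cohort found no evidence that surgery improved outcomes. Bias needs gradability to differ by arm and to be related to deformity; with equal shares the odds ratio is 1.0. This stands, so the point is a conditional risk.

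**No loss rate is given.** One might also infer that 10-30% of hips will drop out of the analysis. That only restates assumed shares. This stands.

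**The protocol already has part of the answer.** Waldenström grade is recorded centrally, and section 23.8 covers all secondary outcomes, with imputation if missingness is differential. This stands in part. Section 23.8 does not mention hips that are imaged but too early to grade, and these may not be counted as missing at all.

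**Imputation is not a clean cure.** If reaching 3B/4 depends on the unseen grade, imputation under missing at random does not remove the bias. This stands, and imputation should not become the main analysis.

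**Waiting for healing may be clinically sensible, and the date slip is small.** Both are fair. Appendix 2 harvests all routine images, so the 36-month image can still be chosen. The slip adds no weight to the selection argument.

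**Conclusion.** The point holds as a defect in what the protocol itself fixes: all hips enter before re-ossification, only those at 3B/4 receive a Stulberg grade, and that grade is the only deformity measure compared by arm. Hips not yet at 3B/4 have no stated place in the comparison, which is therefore conditional on a post-randomisation state.

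Whether it is biased is unknown. With no true effect, the illustrative odds ratio is 1.0 for equal shares and about 1.05 to 1.5 for shares differing by 10-20 points, with slopes of 0.3 to 1.5 log-odds per SD. Shares and slopes are assumptions, and the direction depends on which arm reaches 3B/4 in greater numbers. At a slope of 1.0 and 90% v 75%, the shift is below one standard error. The primary outcome and the sample size are untouched. The conflict over the image date is certain from the text, but small. This is a cheap improvement to one secondary outcome.

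**What to change.** 1. In section 23.3.2 (and the SAP), compare the proportion of hips at Waldenström 3B or 4 at 36 months by arm, using the stage already recorded at central review.
2. Keep the ordinal model in gradable hips, but label it as conditional on reaching 3B/4. Add a sensitivity analysis over all randomised hips with an image, ranking not-yet-gradable hips best and then worst, or placing them in a separate category. Use multiple imputation of the grade only as a further sensitivity analysis.
3. Reconcile Appendix 2 with Table 7 and sections 9.5 and 20, so that the image is anchored on 36 months after randomisation in both arms.

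Cost: protocol and SAP wording and a few more analysis lines. No new images or readers are needed. The downside is a less simple report for this outcome.
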